10.0 CRITERIA FOR EVALUATION AND ENDPOINT ANALYSIS

10.1 Measurability of lesions

- a. **Measurable disease:** Measurable disease is defined differently for lymph nodes compared with other disease and will be addressed in a separate section below.
1. Lesions that can be accurately measured in at least one dimension (longest diameter to be recorded) as ≥ 2.0 cm by chest x-ray, by ≥ 1.0 cm with CT or MRI scans, or ≥ 1.0 cm with calipers by clinical exam. All tumor measurements must be recorded in decimal fractions of centimeters (or millimeters).

The defined measurability of lesions on CT scan is based on the assumption that CT slice thickness is 0.5 cm or less. If CT scans have slice thickness greater than 0.5 cm, the minimum size for a measurable lesion should be twice the slice thickness.
 2. **Malignant lymph nodes** are to be considered pathologically enlarged and measurable if it measures ≥ 1.5 cm in **SHORT AXIS** (greatest diameter perpendicular to the long axis of the lymph node) when assessed by scan (CT scan slice recommended being no greater than 0.5 cm).
- b. **Non-measurable disease:** All other lesions (or sites of disease), including small lesions (longest diameter < 1.0 cm or pathologic lymph nodes with ≥ 1.0 cm to < 1.5 cm short axis), are considered non-measurable disease. Bone lesions, leptomeningeal disease, ascites, pleural/pericardial effusions, lymphangitis cutis/pulmonitis, inflammatory breast disease, and abdominal masses (not followed by CT or MRI), are considered non-measurable as are previously radiated lesions that have not progressed.
- c. **Notes on measurability**
1. For CT and MRIs, the same type of scanner should be used, and the image acquisition protocol should be followed as closely as possible to prior scans. Body scans should be performed with breath-hold scanning techniques, if possible.
 2. PET-CT: At present, the low dose or attenuation correction CT portion of a PET-CT is not always of optimal diagnostic CT quality for use with RECIST measurements. Therefore, PET-CT is not allowed as an imaging modality for S1801. Extremity melanomas must be imaged using CT with intravenous contrast or MRI with and without gadolinium.
 3. Ultrasound: Ultrasound is not useful in assessment of lesion size and should not be used as a method of measurement.
 4. Cystic lesions that meet the criteria for radiographically defined simple cysts should not be considered as malignant lesions (neither measurable nor non-measurable) since they are, by definition simple cysts.
 5. If a target lesion becomes very small some radiologists indicate that it is too small to measure. If the lesion is actually still present, a default measurement of 0.5 cm should be applied. If the radiologist believes the lesion has gone, a default measurement of 0.0cm should be recorded.

10.2 **RECIST Objective status at each disease evaluation:**

Objective Status is to be recorded at each evaluation. All measurable lesions up to a maximum of 2 lesions per organ 5 lesions in total, representative of all involved organs, should be identified as target lesions at baseline. All other lesions (or sites of disease) including any measurable lesions over and above the 5 target lesions should be identified as non-target lesions. Measurements must be provided for target measurable lesions, while presence or absence must be noted for non-target measurable and non-measurable disease.

For studies that use disease progression as an endpoint, whole body scanning at specific intervals is necessary to determine that progression is NOT present outside of the “target” areas. Therefore, in these studies it is not acceptable to image only the “target” areas of the body in follow-up scans. For study-specific imaging requirements, see the Study Calendar in [Section 9.0](#).

- a. **Complete Response (CR):** Complete disappearance of all target and non-target lesions (with the exception of lymph nodes mentioned below). No new lesions. No disease related symptoms. Any lymph nodes (whether target or non-target) must have reduction in short axis to < 1.0 cm. All disease must be assessed using the same technique as baseline.
- b. **Partial Response (PR):** Applies only to participants with at least one measurable lesion. Greater than or equal to 30% decrease under baseline of the sum of appropriate diameters of all target measurable lesions. No unequivocal progression of non-measurable disease. No new lesions. All target measurable lesions must be assessed using the same techniques as baseline.
- c. **Stable:** Does not qualify for CR, PR, Progression or Symptomatic Deterioration. All target measurable lesions must be assessed using the same techniques as baseline.
- d. **Progression:** One or more of the following must occur: 20% increase in the sum of appropriate diameters of target measurable lesions over smallest sum observed (over baseline if no decrease during therapy) using the same techniques as baseline, as well as an absolute increase of at least 0.5 cm. Unequivocal progression of non-measurable disease in the opinion of the treating physician (an explanation must be provided). Appearance of any new lesion/site. Death due to disease without prior documentation of progression and without symptomatic deterioration (see [Section 10.2e](#)).

Notes regarding new lesions: FDG-PET imaging can complement regular scans in identifying new lesions according to the following algorithm.

1. Negative FDG-PET at baseline, with a positive FDG-PET at follow-up is a sign of progression based on a new lesion.
 2. No FDG-PET at baseline and a positive FDG-PET at follow-up corresponding to a potential new site of disease must have a confirmation by anatomical assessment (e.g. CT, MRI, x-ray) as new site of disease to be considered progressive disease. In such a case, the date of progressive disease will be the date of the initial abnormal FDG-PET.
- e. **Symptomatic deterioration:** Global deterioration of health status requiring discontinuation of treatment without objective evidence of progression. Efforts should be made to obtain objective evidence of progression after discontinuation.

f. **Assessment inadequate, objective status unknown.** Progression or symptomatic deterioration has not been documented, and one or more target measurable lesions have not been assessed or inconsistent assessment methods were used.

g. **Objective status notes**

1. Non-measurable and non-target measurable disease do not affect Objective Status in determination of CR (must be absent--a participant who otherwise has a CR, but who has non-measurable or non-target measurable disease present or not assessed, will be classified as having a PR). However, non-measurable and non-target lesions are included in determination of progression (if new sites of disease develop or if unequivocal progression occurs in the opinion of the treating physician).
2. An objective status of PR or stable cannot follow one of CR. Stable can follow PR only in the rare case that tumor increases too little to qualify as progression, but enough that a previously documented 30% decrease no longer holds.
3. In cases for which initial flare reaction is possible (hypercalcemia, increased bone pain, erythema of skin lesions), objective status is not progression unless either symptoms persist beyond 4 weeks or there is additional evidence of progression.
4. Lesions that appear to increase in size due to presence of necrotic tissue will not be considered to have progressed.
5. For bone disease documented on bone scan only, increased uptake does not constitute unequivocal progression. However, increase in the soft tissue component of a lesion as measured by CT or MRI would constitute progression.
6. Appearance of new pleural effusions does not constitute unequivocal progression unless cytologically proven of neoplastic origin, since some effusions are a toxicity related to therapy or other medical conditions. Increase in the size of an existing effusion does not constitute unequivocal progression, since the fluid status of the participant could alter the size of the effusion.
7. If CR determination depends on a lesion for which the status is unclear by the required tests, it is recommended the residual lesion be investigated with biopsy or fine needle aspirate.

10.3 **RECIST Best Response.** This is calculated from the sequence of objective statuses.

- a. CR: Two or more objective statuses of CR a minimum of four weeks apart documented before progression or symptomatic deterioration.
- b. PR: Two or more objective statuses of PR or better a minimum of four weeks apart documented before progression or symptomatic deterioration, but not qualifying as CR.
- c. Unconfirmed CR: One objective status of CR documented before progression or symptomatic deterioration but not qualifying as CR or PR.

- d. Unconfirmed PR: One objective status of PR documented before progression or symptomatic deterioration but not qualifying as CR, PR or unconfirmed CR.
- e. Stable/no response: At least one objective status of stable/no response documented at least 6 weeks after registration and before progression or symptomatic deterioration, but not qualifying as anything else above.
- f. Increasing disease: Objective status of progression within 12 weeks of registration, not qualifying as anything else above.
- g. Symptomatic deterioration: Objective status of symptomatic deterioration within 12 weeks of registration, not qualifying as anything else above.
- h. Inadequate assessment, response unknown: Progression or symptomatic deterioration greater than 12 weeks after registration and no other response category applies.

10.4 Progression before surgery

- a. Progression of disease per RECIST 1.1 before surgery such that the participant cannot receive the planned surgery or requires additional surgery.

Note: Progression of disease that maintains the ability to undergo the planned surgery is not criteria for removal from treatment.

10.5 Relapse after surgery

Appearance of any new metastatic lesion/site.

- a. Appearance of a new melanoma in-situ or Stage I melanoma which can be treated curatively by wide excision does not constitute recurrence. If this does occur, upload pathology and operative reports via the Source Documentation: Follow-Up Form in Rave.
- b. Any enlargement in lymph nodes >1 cm in short axis and >50% from baseline must be biopsied to rule out relapse of disease.
- c. Appearance of new pleural effusions does not constitute unequivocal progression unless cytologically proven of neoplastic origin, since some effusions are a toxicity related to therapy or other medical conditions. Increase in the size of an existing effusion does not constitute unequivocal progression, since the fluid status of the participant could alter the size of the effusion.

Notes regarding new lesions: FDG-PET imaging can complement regular scans in identifying new lesions according to the following algorithm.

1. Negative FDG-PET at baseline, with a positive FDG-PET at follow-up is a sign of progression based on a new lesion.
2. No FDG-PET at baseline and a positive FDG-PET at follow-up corresponding to a potential new site of disease must have a confirmation by anatomical assessment (e.g. CT, MRI, X-ray) as new site of disease to be considered progressive disease. In such a case, the date of progressive disease will be the date of the initial abnormal FDG-PET.

10.6 Pathologic Response

In prior studies using neoadjuvant targeted (BRAF/MEK inhibitor) and neoadjuvant immune checkpoint blockade therapy, previously agreed upon standard definitions of pathologic response are:

- **Complete pathologic response (path CR):** the complete absence of viable tumor cells in the surgically resected post-treatment specimen.
- **Partial pathologic response (path PR):** admixture of viable tumor cells but these comprise less than 50% of the treated tumor bed surface area together with evidence of treatment effect, including necrosis, fibrosis, and a lymphohistiocytic inflammatory infiltrate including aggregates of pigmented macrophages (tumoral melanosis).
- **Pathologic non-response (path NR):** admixture of viable tumor cells and these comprise greater than 50% of the treated tumor bed surface area together with evidence of treatment effect, including necrosis, fibrosis, and a lymphohistiocytic inflammatory infiltrate including aggregates of pigmented macrophages (tumoral melanosis).

10.7 **IRECIST Objective status at each disease evaluation:**

Objective Status is to be recorded at each evaluation. All measurable lesions up to a maximum of 2 lesions per organ 5 lesions in total, representative of all involved organs, should be identified as *target* lesions at baseline All other lesions (or sites of disease) including any measurable lesions over and above the 5 target lesions should be identified as *non-target* lesions. Measurements must be provided for target measurable lesions, while presence or absence must be noted for non-target measurable and non-measurable disease.

New lesions: All measurable lesions not present at baseline up to a maximum of 2 lesions per organ 5 lesions in total, representative of all involved organs, should be identified as new target lesions (NTL). All other new lesions (not present at baseline) including any measurable new lesions over and above the 5 new target lesions should be identified as new lesions, non-target (NLNT). Measurements must be provided for NTL, while presence or absence must be noted for NLNT.

- a. **Complete Response (CR):** Complete disappearance of all target and non-target lesions (with the exception of lymph nodes mentioned below). No new lesions. No disease related symptoms. Any lymph nodes (whether target or non-target) must have reduction in short axis to < 1.0 cm. All disease must be assessed using the same technique as baseline.
- b. **Partial Response (PR):** Applies only to participants with at least one measurable lesion. Greater than or equal to 30% decrease under baseline of the sum of appropriate diameters of all target measurable lesions. No unequivocal progression of non-measurable disease. No new lesions. All target measurable lesions must be assessed using the same techniques as baseline.
- c. **Stable:** Does not qualify for CR, PR, Progression or Symptomatic Deterioration. All target measurable lesions must be assessed using the same techniques as baseline.

- d. **Immune-related Unconfirmed Progression (iUPD):** One or more of the following must occur: 20% increase in the sum of appropriate diameters of target lesions over smallest sum observed (over baseline or nadir) using the same techniques as baseline, as well as an absolute increase of at least 0.5 cm. Do not include the sum of diameters of NTL. Unequivocal progression of non-measurable disease in the opinion of the treating physician (an explanation must be provided). Appearance of any new lesion/site. Death due to disease without prior documentation of progression and without symptomatic deterioration.

Notes regarding new lesions: FDG-PET imaging can complement regular scans in identifying new lesions according to the following algorithm.

Negative FDG-PET at baseline, with a positive FDG-PET at follow-up is a sign of progression based on a new lesion.

No FDG-PET at baseline and a positive FDG-PET at follow-up corresponding to a potential new site of disease must have a confirmation by anatomical assessment (e.g. CT, MRI, x-ray) as new site of disease to be considered progressive disease. In such a case, the date of progressive disease will be the date of the initial abnormal FDG-PET.

- e. **Immune-related Confirmed Progression (iCPD):** Can only be reported in the assessment immediately following iUPD. One or more of the following must occur:
- An absolute increase of at least 0.5 cm in the sum of target lesions over the sum observed at iUPD. Do not include the sum of diameters of NTL
 - An absolute increase of at least 0.5 cm in the sum of NTL over the sum observed at iUPD. Do not include the sum of diameters of target lesions.
 - Clear worsening of unequivocal progression of non-measurable disease in the opinion of the treating physician as documented at iUPD (an explanation must be provided).
 - Unequivocal progression, in the opinion of the treating investigator, of new non-target lesions (NNTL) initially documented at iUPD
 - Any additional cause of progression, as defined in [10.7a](#), that was not present at iUPD.
- f. **Immune-related Complete Response (iCR):** Can only occur after an assessment of iUPD, but not necessarily in the assessment immediately following iUPD. Cannot occur after iCPD. Complete disappearance of all lesions (with the exception of lymph nodes mentioned below). No new lesions. No disease related symptoms. Any lymph nodes (whether target, non-target, NTL, or NLNT) must have reduction in short axis to < 1.0 cm. All disease must be assessed using the same technique as baseline.
- g. **Immune-related Partial Response (iPR):** Can only occur after an assessment of iUPD, but not necessarily in the assessment immediately following iUPD. Cannot occur after iCPD. Applies only to participants with at least one measurable lesion at baseline. Greater than or equal to 30% decrease under baseline of the sum of appropriate diameters of all target lesions present at baseline. Do not include the sum of diameters of NTL. No unequivocal progression of non-measurable disease. No new lesions other than those documented at iUPD. No increase in the sum of diameters of NTL, or an increase of less than 0.5 cm. All target lesions must be assessed using the same techniques as baseline.

- h. **Immune-related Stable Disease (iSD)**: Can only occur after an assessment of iUPD, but not necessarily in the assessment immediately following iUPD. Cannot occur after iCPD. Does not qualify for iCR, iPR, iUPD or Symptomatic Deterioration. All target measurable lesions must be assessed using the same techniques as baseline.
- i. **Symptomatic deterioration**: Global deterioration of health status requiring discontinuation of treatment without objective evidence of progression. Efforts should be made to obtain objective evidence of progression after discontinuation.
- j. **Assessment inadequate, objective status unknown**. Progression or symptomatic deterioration has not been documented, and one or more target measurable lesions have not been assessed or inconsistent assessment methods were used.

10.8 Objective status notes

Non-measurable disease does not affect objective Status in determination of iCR (must be absent--a participant who otherwise has a iCR, but who has non-measurable disease present or not assessed, will be classified as having an iPR). However, non-measurable lesions are included in determination of iPD (if new sites of disease develop or if unequivocal progression occurs in the opinion of the treating physician).

- a. An objective status of iPR or irD cannot follow one of iCR. iSD can follow iPR only in the rare case that tumor increases too little to qualify as iPD, but enough that a previously documented 30% decrease no longer holds.
- b. In cases for which initial flare reaction is possible (hypercalcemia, increased bone pain, erythema of skin lesions), objective status is not iPD unless either symptoms persist beyond 4 weeks or there is additional evidence of progression.
- c. Lesions that appear to increase in size due to presence of necrotic tissue will not be considered to have progressed.
- d. For bone disease documented on bone scan only, increased uptake does not constitute unequivocal iPD. However, increase in the soft tissue component of a lesion as measured by CT or MRI would constitute ir-progression.
- e. Appearance of new pleural effusions does not constitute unequivocal iPD unless cytologically proven of neoplastic origin, since some effusions are a toxicity related to therapy or other medical conditions. Increase in the size of an existing effusion does not constitute unequivocal iPD, since the fluid status of the participant could alter the size of the effusion.
- f. If iCR determination depends on a lesion for which the status is unclear by the required tests, it is recommended the residual lesion be investigated with biopsy or fine needle aspirate.

10.9 iRECIST Best Response

This is calculated from the sequence of iRECIST objective statuses. (12)

- a. CR: Two or more objective statuses of CR a minimum of four weeks apart documented before iUPD or symptomatic deterioration.

- b. PR: Two or more objective statuses of PR or better a minimum of four weeks apart documented before iUPD or symptomatic deterioration, but not qualifying as CR.
- c. Unconfirmed CR: One objective status of CR documented before progression or symptomatic deterioration but not qualifying as CR or PR.
- d. Unconfirmed PR: One objective status of PR documented before progression or symptomatic deterioration but not qualifying as CR, PR or unconfirmed CR.
- e. Stable/no response: At least one objective status of stable/no response documented at least 6 weeks after registration and before iUPD or symptomatic deterioration, but not qualifying as anything else above.
- f. iCR: Two or more objective statuses of iCR a minimum of four weeks apart documented before iCPD or symptomatic deterioration, but not qualifying as CR.
- g. iPR: Two or more objective statuses of iPR or better a minimum of four weeks apart documented before iCPD or symptomatic deterioration, but not qualifying as iCR, CR or PR.
- h. Unconfirmed iCR: One objective status of iCR documented before iCPD or symptomatic deterioration but not qualifying as CR, PR, unconfirmed CR, iCR or iPR.
- i. Unconfirmed iPR: One objective status of iPR documented before iCPD or symptomatic deterioration but not qualifying as CR, PR, unconfirmed CR, unconfirmed PR, iCR, iPR or unconfirmed iCR.
- j. iSD: At least one objective status of iSD before iCPD or symptomatic deterioration, but not qualifying as anything else above.
- k. iUPD: Objective status of iUPD within 12 weeks of registration, before symptomatic deterioration or iCPD and not qualifying anything else above. There can be multiple IUPD assessments with no iCPD when the original cause of iUPD persists and no new causes of progression appear.
- l. iCPD: An objective status of iCPD, which must be documented a minimum of four weeks apart from and immediately follow an objective status of iUPD and must be documented before symptomatic deterioration.
- m. Symptomatic deterioration: Objective status of symptomatic deterioration within 12 weeks of registration, not qualifying as anything else above.
- n. Inadequate assessment, response unknown: Progression or symptomatic deterioration greater than 12 weeks after registration and no other response category applies

10.10 Event-Free Survival

Measured from date of randomization to date of first: documentation of progression that renders participant unable to receive planned protocol surgery, off protocol therapy for any reason without subsequent protocol surgery (with one exception noted below), failure to begin adjuvant therapy within 84 days after surgery, relapse after surgery or death due to any cause. Participants last known to be alive and event-free are censored at date of last contact. On both arms, all participants who do not register for adjuvant therapy (for whatever reason) will be assigned the event time of 84 days.

Patients treated on the neo-adjuvant arm who achieve an unconfirmed PR or CR (per RECIST 1.1) at the first protocol disease assessment and choose not to undergo protocol surgery will not be counted as an event if the PR or CR is confirmed prior to starting any non-protocol therapy other than pembrolizumab. Such patients will not have an event when not receiving protocol surgery, and their EFS will be measured from the date of randomization to the first of relapse or death due to any causes with patients last known to be alive without relapse censored at the date of last contact. All other patients who do not receive protocol surgery will be assigned the EFS event time of 84 days.

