 - c. Post-treatment follow-up (prior to relapse): Participants should be seen at 3 weeks (-/+ 1 week) after the last dose, then 12 weeks (-/+ 1 week) after the last dose, then every 3 months (+/- 2 weeks) if participant is < 2 years from study entry, every 6 months (+/- 4 weeks) if participant is 2-5 years from study entry, and every 12 months (+/- 4 weeks) if participant is > 5 years from study entry for up to 10 years. The first two follow-up visits may be scheduled to allow follow-up visits and scans to occur on the same date for on-going follow-up. The following exams and labs should be performed: physical (including BP & wt), and PS. For post-treatment follow-up regarding scans, see footnote [k](#).
 - d. Follow-up post progression/relapse: Participants who develop recurrent melanoma or who have progression of disease such that the participant cannot receive their planned surgery or require additional surgery will be followed for survival (vital status). Participants should be followed every 6 months for up to 2 years from the date of progression/relapse, then annually thereafter until 10 years from treatment randomization.
 - e. While on study, blood collected for pretreatment laboratory tests must be collected and analyzed no more than 3 days prior to dosing. NOTE: if pembrolizumab (MK-3475) was delayed per the dose delay/scheduling criteria or if a visit had to be delayed due to major circumstances (such as a health emergency, family/personal emergency, transportation difficulties, scheduling difficulties; a visit date falls on a holiday), the study assessments scheduled for these dates will be delayed.
 - g. Treatment and visits should continue at these intervals through Cycle 18.
 - h. Adverse Event Assessments on the study will continue for all participants until 30 days after the last study drug administration. However, participants with ongoing toxicities should be seen more often as clinically indicated.
 - i. Women of child bearing potential must have a negative serum or urine pregnancy test at screening within 28 days prior to randomization. Following randomization, serum or urine pregnancy tests are required within 72 hours prior to the first dose of study treatment, then according to institutional practice during therapy. Tests should coincide with clinic visits for blood work and ending with the discontinuation of study treatment. A pregnancy test should be done at any time there are clinical concerns for possible pregnancy.

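### For neoadjuvant responders who decline surgery, EFS ends only at relapse or death, so regrowth of unresected tumor after a partial response is not, as written, an event

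*Combined protocol and SAP*

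**What the plan says.** Section 10.10 (Event-Free Survival) has a general event list and one exception.

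- **General list.** Before surgery, progression counts in the form "documentation of progression that renders participant unable to receive planned protocol surgery". Relapse after surgery is listed as a separate event.
- **Exception.** It covers neoadjuvant-arm patients who respond (PR or CR by RECIST 1.1) at the first assessment, choose not to have protocol surgery, and have the response confirmed before any outside therapy other than pembrolizumab. For them, "their EFS will be measured from the date of randomization to the first of relapse or death due to any causes". Those alive without relapse are censored at last contact.
- **Day-84 sentences.** One says that "all participants who do not register for adjuvant therapy (for whatever reason) will be assigned the event time of 84 days". The section closes with "All other patients who do not receive protocol surgery will be assigned the EFS event time of 84 days".

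The terms are defined elsewhere in Section 10:

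- Section 10.5, headed as relapse after surgery: "Appearance of any new metastatic lesion/site".
- Section 10.2d, progression by growth of existing lesions: "20% increase in the sum of appropriate diameters of target measurable lesions over smallest sum observed", with an absolute increase of at least 0.5 cm.
- Section 10.4, progression before surgery: "Progression of disease per RECIST 1.1 before surgery such that the participant cannot receive the planned surgery or requires additional surgery".

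**The concern.** A patient with a confirmed PR who declines surgery still has tumor in place. Regrowth of that tumor is an obvious way for treatment to fail, yet the exception does not name it. Under the text as it stands, such a patient stays at risk or is censored until a new lesion appears or the patient dies. The failure is then counted late or not at all.

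This is the primary endpoint, and only the neoadjuvant arm has the exception. Any undercount therefore works in one direction, toward the experimental arm. If the rule stays unwritten, each case has to be settled by judgment for patients already known to be on that arm.

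The gap mainly concerns PR. Reappearance of disease after a CR is more easily read as relapse.

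**Working it through.** **1. Does any section make regrowth an event for this group?**

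| Place | What it covers | Reaches growth of an existing, unresected lesion? |
|---|---|---|
| 10.10, exception | relapse or death | Only if relapse includes it |
| 10.5 | new metastatic lesion or site, after surgery | No: neither new nor after surgery |
| 10.5b | biopsy of enlarging nodes | Partly: a biopsy trigger, for nodes only |
| 10.10, general list | progression that rules out planned surgery | Unclear once surgery has been declined; the exception also states its own rule |
| 10.4 | the same, or additional surgery required | Unclear for the same reason |
| 10.2d | RECIST 1.1 progression | Yes, but the exception does not refer to it |

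Study Calendar footnote d also keeps the two terms apart and ties progression to surgery: "Participants who develop recurrent melanoma or who have progression of disease such that the participant cannot receive their planned surgery", or who require additional surgery. No row makes regrowth an EFS event for this group.

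**2. The plan's own figure.** Inputs from Section 11.2: 104 events, average hazard ratio 0.64, two-sided 15% log-rank test (z = 1.4395), stated power 81%. By the Schoenfeld formula:

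Φ(√104/2 × |ln 0.64| − 1.4395) = Φ(5.099 × 0.4463 − 1.4395) = Φ(0.836) = 79.8%

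Simulating the stated cure models with 250 per arm and 2-year accrual gives 83%. Both lie within 2 points of 81%, so the test set-up is understood correctly.

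**3. Effect of uncounted events under the null.** With 104 events, 52 are expected per arm. If x neoadjuvant events go uncounted, observed minus expected on that arm shifts by x/2, with variance (104 − x)/4. The z shift is (x/2)/√((104 − x)/4) = x/√(104 − x). The one-sided error favoring neoadjuvant is 1 − Φ(1.4395 − shift), and the apparent hazard ratio is exp(−(x/2)/((104 − x)/4)).

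| x (assumed) | Shift | One-sided error | Apparent HR |
|---|---|---|---|
| 0 | 0 | 7.5% | 1.00 |
| 1 | 1/√103 = 0.0985 | 9.0% | 0.98 |
| 2 | 2/√102 = 0.198 | 10.7% | 0.96 |
| 4 | 4/√100 = 0.400 | 14.9% | 0.92 |

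**4. How many exception patients would that take?** The planned event fraction is 104/336 = 31% (336 patients from Section 11.3). If every failure were regrowth in place and never counted later, x = 1 needs 1/0.31 ≈ 3 patients, x = 2 needs about 6, and x = 4 needs about 13, or 13/168 = 8% of the arm. If half of failures were in place, the numbers double. The x = 4 row is therefore an extreme.

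**5. A milder scenario by simulation.** Assume 336 patients, 3.5-year accrual, analysis at 104 counted events, exception patients failing at half the arm's rate, and half of those failures in place. With 2, 4 or 8 exception patients the error is 7.6%, 8.2% or 8.6%, against 7.4% with none (Monte Carlo standard error 0.12 to 0.15 points). The accrual period is assumed, so this is only a rough check that the effect is small when such patients are few.

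**The case against.** The case for leaving the text alone has real content.

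- **The two words are not kept strictly apart.** Section 10.5 itself speaks of progression in its effusion and FDG-PET clauses. Section 10.5b sends enlarging nodes to biopsy to rule out relapse, so a biopsy-positive enlarging node would probably be treated as relapse. The exception also drops the after-surgery qualifier that the general list attaches to relapse, so a wider meaning may be intended. This narrows the gap. It does not close it: no wider meaning is stated, 10.5b is limited to nodes and is not an event definition, and the general list in 10.10 names progression and relapse separately.
- **The data are captured either way.** Section 14.3d asks for a form on sites of progression or relapse within 15 days of either. That is true and makes the fix cheap, but collecting a progression does not make it an EFS event.
- **The numbers affected are probably few.** Entry to the exception is narrow. Section 2.0 says distant relapses exceed half of relapse events in Stage III, and new distant lesions and deaths count even on the narrowest reading. This stands, and it is why the larger values in the working should not be taken as likely.

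A reader might also infer that exempt patients become events at day 84, because Step 3 registration requires surgery (Section 5.3a) and the sentence on not registering for adjuvant therapy allows no exceptions. The documents do not support that. The general list announces an exception, the exception says these patients have no event for missing surgery, and the closing sentence is limited to all other patients. Only a cross-reference is missing.

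**Conclusion.** The point holds for the primary-endpoint definition. As written, growth of unresected tumor after a PR in a neoadjuvant patient who declines surgery is not an EFS event unless a new lesion or death follows, and the omission can favor only the neoadjuvant arm.

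A reader might go further and infer that the plan deliberately excludes regrowth, or that the primary comparison is materially biased. Neither is supported. The text leaves relapse undefined for unresected patients, and the documents do not say how many patients use the exception. On assumed counts of 1 or 2 uncounted events, the one-sided error is 9.0% or 10.7% instead of 7.5%. With few such patients and low failure rates the effect is negligible. It should be fixed because the rule sits in the primary endpoint, acts on one arm only, and can be settled in a sentence.

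**What to change.** In Section 10.10:

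1. For patients under the exception, define the event as the first of RECIST 1.1 progression (10.2d, including growth of unresected disease or a new lesion), relapse, or death from any cause, with censoring at last contact otherwise. RECIST 1.1 is the natural choice because the exception already uses it for entry, but any explicit rule would close the gap.
2. Add *except as noted below* to the sentence assigning day 84 to all who do not register for adjuvant therapy. This is a wording correction only.
3. Report the number of exception patients and how many had progression without relapse. Run the EFS log-rank test with and without those progressions counted as events. The per-protocol analyses in Section 11.4 do not name this group or its event rule.

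**Cost.** Two wording changes and one sensitivity analysis. No new scans or forms are needed: neoadjuvant patients without surgery already have scheduled assessments (Section 7.4, Study Calendar footnote q), and Sections 14.3a and 14.3d already collect the results.

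**Downside.** A few more neoadjuvant events may be counted. Progression would also be judged more strictly here than for patients still awaiting surgery, for whom progression that leaves the planned surgery possible is not an event. The amended text should acknowledge that difference.
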